3. STUDY DESIGN OVERVIEW

Sequential Allocation of Subject Numbers	
	Fluarix Tetra (N=max 1,440 (720 vaccinees \geq 3 years old, 720 vaccinees between 6-35 months old))
Vaccination (Fluarix Tetra)	Drug Use Investigation Conclusion 21 days (Day 0 to Day 20) follow-up after vaccination with Fluarix Tetra
N: Number of subjects planned to be enrolled	

Drug use investigation conclusion will depend on the 21 days contact of the subject in the drug use investigation. Definition of Conclusion of drug use investigation for a subject: A subject who is available for the concluding follow-up contact 21 days (Day 0 to Day 20) after receiving *Fluarix Tetra* is considered to have completed the drug use investigation.

- Drug use investigation design: A prospective, observational, non-comparative, multi-center study in Korea.
- Vaccination schedule: Vaccination as per locally approved PI (which is not part of the drug use investigation): to adults and previously vaccinated children aged \geq 6 months, a single 0.5 ml dose of *Fluarix Tetra* will be administered. To previously unvaccinated children aged 6 months to $<$ 9 years, two doses will be administered with a second 0.5 ml dose at least 4 weeks apart from the first one as per the local PI in Korea.

Fluarix Tetra may be administered to pregnant women/lactating women as per PI, if there is a clear need. Pregnancy outcome (whether full-term or premature, information on the status of the mother and child) in vaccinated pregnant subjects will be followed-up at 6-8 weeks after delivery, if possible.

Note:

- Vaccination with *Fluarix Tetra* is not part of the drug use investigation.
- Signature of the subject/subject's parent(s)/LAR(s) on the ICF/IAF signify enrolment of the subject into the drug use investigation. The ICF/IAF is for the collection and handling of safety information and not for the vaccination procedure.

- Administration of vaccines included in the EPI and other licensed vaccines are allowed in this drug use investigation regardless of the time of administration.
- Safety monitoring:
 - Recording of all AEs during the 21 days (Day 0 to Day 20) using diary cards after *Fluarix Tetra* is administered.
 - The participating physician will transcribe the collected information into the CRF in English.
 - ***Recording of all ADRs reported during the 21 days (Day 0 to Day 20) follow-up period after administration of Fluarix Tetra***

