7.2.2.3. Assessment of causality

The physician is obligated to assess the relationship between *Fluatrix Tetra* and the occurrence of each AE/SAE. The physician will use clinical judgement to determine the relationship. Alternative plausible causes, based on natural history of the underlying diseases, concomitant therapy, other risk factors, and the temporal relationship of the event to *Fluarix Tetra* will be considered and investigated. The physician will also consult the local PI for marketed products in the determination of his/her assessment of AEs.

There may be situations when a SAE has occurred and the physician has minimal information to include in the initial report to GSK Vaccines. However, it is very important that the physician always makes an assessment of causality for every event prior to submission of the SAE to GSK Vaccines. The physician may change his/her opinion of causality in light of follow-up information, amending the SAE information accordingly. The causality assessment is one of the criteria used when determining regulatory reporting requirements.

In case of concomitant administration of multiple vaccines, it may not be possible to determine the causal relationship of general AEs to the individual vaccines administered. The physician should, therefore, assess whether the AE could be causally related to vaccination rather than to the individual vaccines.

Causality of AEs should be assessed by the physician using the following question:

Is there a reasonable possibility that the AE may have been caused by *Fluarix Tetra*?

Non-serious and serious AEs will be evaluated as two distinct events. If an event meets criteria to be determined ‘serious’ (see Section 7.1.3), additional examinations/tests will be performed by the physician in order to determine ALL possible contributing factors applicable to each SAE.

Possible contributing factors include:

- Medical history
- Other medication
- Protocol required procedure
- Other procedure not required by the protocol
- Lack of efficacy of the vaccine(s), if applicable
- Erroneous administration
- Other cause (specify)

NOTE: The use of the term “drug” here refers to *Fluarix Tetra*.

The relationship of the drug to an AE will be determined by the physician based on the following definitions:

1. Certain:

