 - The relationship of the administration and use of the drug is reasonable and it is not able to be explained by other medication, chemical substances or concomitant disease, it shows clinically reasonable response on withdrawal of the drug, the decisive case in the pharmacological or phenomenological aspect on re-challenge of the drugs if needed.
2. Probable/Likely:
 - The temporal sequence of the administration and use of the drug is appropriate and it does not seem that it is accompanied by other medications, chemical substances or concomitant disease, in the case that shows clinically appropriate response on withdrawal of the drug (no information for re-challenge).
3. Possible:
 - The temporal sequence of the administration and use of the drug is appropriate but it is also able to be explained by other medications, chemical substances or concomitant disease, and information related to withdrawal of the drug is insufficient or vague.
4. Not-Related:

- The AE is not related to the drug if there is evidence that clearly indicates an alternative explanation. If the subject has not received the drug, the timing of the exposure to the drug and the onset of the AE are not reasonably related in time, or other facts, evidence or arguments exist that reasonably suggest an alternative explanation, then the AE is not related.

5. Conditional/Unclassified:

- In the case that more information is needed for a proper evaluation or additional information is under review.

6. Unassessable/Unclassifiable:

- In the case that could not be judged due to insufficient or conflicting information and no way to complement or validate.

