### 6.2 Subject characteristics

Data for the subject characteristics is demonstrated by descriptive statistics for safety analysis set.

In the descriptive statistics, number of subjects (N), mean, standard deviation, median, minimum and maximum will be calculated for continuous variables, and frequency and percentage for categorical variables.

The following subject characteristics will be reported:

< Subject baseline Information >

- Gender, Age, Height, Weight, BMI, Ethnicity, General medical history/physical examination

GlaxoSmithKline  
 Protocol No. 204687[EPI-FLU-050 VS KR PMS]

	CONFIDENTIAL : THIS DOCUMENT AND INFORMATION CONTAINED HEREIN IS PROPRIETARY TO COMPANY AND IS NOT TO BE DISCLOSED WITHOUT THE WRITTEN PERMISSION OF COMPANY.	Last Update Date 10-SEP-2021
STATISTICAL ANALYSIS PLAN(V5.0)		

(Past/Current)

< Study Medication Information >

- Vaccination history (influenza vaccination, any non-influenza vaccination), Pre-vaccination body temperature, Dose of Fluarix Tetra administration(All subjects, Subjects under age 9 years\*), Concomitant medication, Concomitant vaccination, Route of concomitant vaccination

< Special Subject Information >

- Pediatric group ( $\geq 3$  years and  $< 19$  years)\*, Elderly group ( $\geq 65$  years)\*, Pregnancy\*, Liver disorder, Kidney disorder

\* Not applicable for study group aged 6-35 months

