### 6.3.2 Adverse Events by Preferred Terms

All AEs recorded in the CRF will be classified by body organs and terms under the classification standard of MedDRA (The most update version of MedDRA at the time of conducting data analysis will be used; the first level is System Organ Class (SOC) and the second level is Preferred Term (PT)) terms, and all AEs excluding the AEs whose causal relation with Fluarix Tetra is ‘Not-Related’ will be treated as AEs whose causal relation cannot be excluded (hereafter “Adverse Drug Reaction (ADR)”).

- ① The number of subjects and the number of AE/ADR, Serious AE/Serious ADR, Unexpected AE/ADR, Unexpected Serious AE/Serious ADR and Unexpected non-serious AE/ADR will be calculated according to the preferred terms. Also, the incidence proportion and its 95% confidence interval using the exact method will be estimated.
- ② Preferred terms of Serious AE/Serious ADR, unexpected AE/ADR will be presented respectively according to the proportion of AE in the local product document.
- ③ For Non-safety analysis set, the number of subjects and the number of AE/ADR, Serious AE/Serious ADR, Unexpected AE/ADR, Unexpected Serious AE/Serious ADR and Unexpected non-serious AE/ADR will be calculated according to the preferred terms. Also, the incidence proportion and its 95% confidence interval using the exact method will be estimated.
- ④ The number and percentage of AE according to the maximum intensity, outcome, relationship to marketed vaccine/product, medically attended visit will be calculated.
- ⑤ All AEs will be classified into the preferred terms according to the maximum intensity, outcome, relationship to marketed vaccine/product, medically attended visit. Also, the number and percentage of each AE will be calculated.

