### 6.3.3 Other Analyses

- ① The distribution of the following will be tabulated with descriptive statistics. Also, 95% confidence interval for the percentage will be estimated using the exact method.
  - Subjects by concomitant medication and pre-existing medical conditions
  - Subjects with concomitant medication by treatment purpose and treatment start date
  - Concomitant medication by treatment purpose and treatment start date
- ② The number of subjects with AE/ADR and the number of AE/ADR by the following will be calculated. Also, the incidence proportion and its 95% confidence interval using the exact method will be estimated.

dreamcis A TIGERMED COMPANY	CONFIDENTIAL : THIS DOCUMENT AND INFORMATION CONTAINED HEREIN IS PROPRIETARY TO COMPANY AND IS NOT TO BE DISCLOSED WITHOUT THE WRITTEN PERMISSION OF COMPANY.	Last Update Date 10-SEP-2021
STATISTICAL ANALYSIS PLAN(V5.0)		

- Concomitant medication and pre-existing medical conditions
- Treatment purpose
- Treatment start date

Note: Pre-existing medical conditions (yes/no) is defined as any significant pre-existing conditions or signs and/or symptoms present prior to the start of the study recorded in the general medical history/physical examination section of the CRF. Treatment purpose of concomitant medication is recorded on the CRF 'Is drug used for treating AE?' of concomitant medication section. Concomitant medication by treatment start date will be classified into yes/no depending on whether concomitant medication started before vaccination.

dreamcis A TIGERMED COMPANY	CONFIDENTIAL : THIS DOCUMENT AND INFORMATION CONTAINED HEREIN IS PROPRIETARY TO COMPANY AND IS NOT TO BE DISCLOSED WITHOUT THE WRITTEN PERMISSION OF COMPANY.	Last Update Date 10-SEP-2021
STATISTICAL ANALYSIS PLAN(V5.0)		

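### Causality has two targets in co-vaccinated subjects, and no ADR table by concomitant vaccination is specified, so the Fluarix Tetra ADR rate may include reactions to other vaccines to an unseen extent

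*Protocol*

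**What the plan says.** **Co-vaccination.** Protocol section 3: "Administration of vaccines included in the EPI and other licensed vaccines are allowed in this drug use investigation regardless of the time of administration". Protocol 6.3.4 and 6.3.4.1 require other vaccines to be recorded in the CRF, over a window from Day -20 to Day 20 around the dose.

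**Causality target.** Protocol 7.2.2.3 notes that with several vaccines "it may not be possible to determine the causal relationship of general AEs to the individual vaccines administered", and draws the consequence: "The physician should, therefore, assess whether the AE could be causally related to vaccination rather than to the individual vaccines". The same section obliges the physician to assess each event against Fluarix Tetra and to weigh concomitant therapy. It poses the question "Is there a reasonable possibility that the AE may have been caused by" Fluarix Tetra, and states that 'drug' in the category definitions means Fluarix Tetra.

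**ADR definition.** SAP 6.3.2 takes "all AEs excluding the AEs whose causal relation with Fluarix Tetra is" 'Not-Related' and labels them ADRs. It has no separate rule for events assessed under the multiple-vaccine instruction.

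**Splits planned.** SAP 6.2 lists "Concomitant medication, Concomitant vaccination, Route of concomitant vaccination" among the subject characteristics. SAP 6.3.1 gives AE counts, AE incidence with 95% CI and an exploratory test by characteristic, leaving out only the route of concomitant vaccination and uncategorised continuous variables. SAP 6.3.3 item 2 does cover ADRs: "The number of subjects with AE/ADR and the number of AE/ADR by the following will be calculated". Its list is concomitant medication and pre-existing conditions, treatment purpose, and treatment start date. Concomitant vaccination is not on it.

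**The concern.** In a subject given only Fluarix Tetra, the two causality targets coincide. In a co-vaccinated subject they can differ. A physician following the multiple-vaccine instruction may rate a fever as possibly related because some vaccine could have caused it. A physician following the question may rate the same fever against Fluarix Tetra alone. Both answers enter one causality field, and the SAP reads that field as relation to Fluarix Tetra.

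ADR incidence by preferred term, with exact 95% CI, is a planned output (Protocol 10.5.2.1, SAP 6.3.2), and the periodic and final statistical reports go to MFDS (Protocol 10.4.1). A reader will take it as describing Fluarix Tetra. If many subjects received other vaccines, which is most plausible at 6-35 months, the rate partly describes those vaccines. The specified ADR tables offer no way to see by how much.

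**Working it through.** **1. Following one event through the plan.** A general AE occurs in a child given Fluarix Tetra and another vaccine on the same day.

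- Under the multiple-vaccine instruction, it is related if any of the vaccines could have caused it.
- Under the question and definitions, it is judged against Fluarix Tetra. If another product could also explain it, 'Possible' still fits: "The temporal sequence of the administration and use of the drug is appropriate but it is also able to be explained by other medications".
- By either route, any rating other than 'Not-Related' makes it a Fluarix Tetra ADR in SAP 6.3.2.
- In SAP 6.3.1 it is counted as an AE by concomitant vaccination. In SAP 6.3.3 item 2 it is counted as an ADR, but by concomitant medication.

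So the gap is specific to ADRs by concomitant vaccination.

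**2. The plan's own precision figures.** Protocol Table 4 gives exact 95% intervals at n=600. Recomputing the Clopper-Pearson interval reproduces all 8 rows to one decimal (for example 5%: 3.4 to 7.1; 10%: 7.7 to 12.7; 15%: 12.2 to 18.1).

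**3. Illustration of size.** Everything below except n=600 is assumed. Let p be the ADR rate due to Fluarix Tetra, c the share co-vaccinated, and q the reaction rate of the other vaccine. Reactions are taken as independent and all other-vaccine reactions as counted, which is the upper end for a given q.

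Reported rate = p + c × q × (1 − p)

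Example: p=5%, c=10%, q=10% gives 0.05 + 0.10 × 0.10 × 0.95 = 5.95%.

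| p | c | q | Reported rate | Exact 95% CI, n=600 | CI excludes p? |
|---|---|---|---|---|---|
| 5% | 10% | 10% | 5.95% | 4.2 to 8.2 | no |
| 5% | 10% | 20% | 6.90% | 4.9 to 9.2 | no |
| 5% | 30% | 5% | 6.4% | 4.7 to 8.8 | no |
| 5% | 30% | 10% | 7.85% | 5.8 to 10.3 | yes |
| 5% | 50% | 20% | 14.5% | 11.8 to 17.6 | yes |
| 10% | 10% | 20% | 11.8% | 9.4 to 14.7 | no |
| 10% | 30% | 10% | 12.7% | 10.1 to 15.6 | yes |
| 10% | 50% | 5% | 12.25% | 9.8 to 15.2 | no |
| 10% | 50% | 20% | 19.0% | 15.9 to 22.4 | yes |

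The full grid was p = 5, 10%; c = 5, 10, 30, 50%; q = 5, 10, 20%. With c of 5% or 10%, the interval covers p in all 12 combinations. With c of 30% or 50%, it excludes p in 9 of 12.

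**4. Sensitivity to the assumptions.** Suppose ADR incidence is 15% after Fluarix Tetra alone. If it is 30% when co-administered, the reported rate is 15 + 15s percent: 16.5%, 19.5% and 22.5% at shares s of 10%, 30% and 50%. It passes Table 4's upper limit of 18.1% once s exceeds 3.1/15 = 21%. If the co-administered incidence is 20%, s must exceed 3.1/5 = 62%. The answer turns on inputs that the documents do not supply.

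**The case against.** The case against has real weight.

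- **The section also asks about Fluarix Tetra.** It does, so a reader who infers that causality is judged only for vaccination as a whole goes too far. What stands is an internal conflict between two targets.
- **'Not-Related' events drop out.** A reader might infer that every event in a co-vaccinated subject becomes an ADR. The documents do not say so: an event with a clear alternative explanation can be rated 'Not-Related', and the reason given for the pooled assessment concerns general AEs.
- **Counting events whose link cannot be excluded is the protocol's own ADR definition** (7.1.2). Agreed, and the overall table should stay. A conservative rule still benefits from showing where it is least specific.
- **Much of the split exists.** AE incidence by concomitant vaccination is planned, so it would be wrong to say there is no split. SAP 6.3.2 items 4 and 5 also show AEs by relationship category and preferred term, which makes doubtful attribution partly visible, but not by vaccination status. SAP 6 plans a final-report analysis by type of concomitant vaccination without naming its outcome. The contents of the mock table appendix are not visible in the public copy, so a planned ADR column there cannot be ruled out.
- **ADR incidence is not an endpoint.** Correct: the endpoints are AEs and SAEs (Protocol 10.1, SAP 4.1). This limits the importance of the point.
- **A same-day split would not isolate Fluarix Tetra.** Also correct. A child given another vaccine the day before would count as having received Fluarix Tetra alone. The strata must use the whole recorded window.

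**Conclusion.** The point holds as a low-cost improvement. Protocol 7.2.2.3 gives two causality targets for co-vaccinated subjects, SAP 6.3.2 treats the answer as relation to Fluarix Tetra, and the SAP text specifies no ADR incidence by concomitant vaccination. The ADR rate may therefore include reactions to other vaccines to an extent the report would not show.

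It is tempting to conclude that the ADR rate will be materially inflated. The documents do not support that, because the co-vaccination share and the other-vaccine reaction rates are both unstated. Under the assumed grid, the effect is within the width of the n=600 interval at about 10% co-vaccinated. It may exceed that at 30% or more, mainly when q is 10% or higher. No figure in the plan is shown to be wrong, and the AE and SAE endpoints are unaffected.

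**What to change.** 1. **Reconcile Protocol 7.2.2.3** so that it states one causality target for co-vaccinated subjects. For assessments already made, say in the report that physicians had both instructions and that the ADR rate in co-vaccinated subjects may reflect vaccination as a whole.
2. **Add concomitant vaccination to the list in SAP 6.3.3 item 2.** Per study group, report subjects with ADRs, incidence and exact 95% CI for three strata: no other vaccine from Day -20 to Day 20; another vaccine on the same day; another vaccine only on other days in that window. Derive the strata from both the vaccination history and the concomitant vaccination records, because Protocol 6.5.3.4 places vaccines given in the preceding 21 days under vaccination history. For children followed after two doses, apply the window to each dose.
3. **Add an ADR table by preferred term** for the stratum with no other vaccine.
4. **Keep the overall ADR table.**

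The cost is one SAP line and a few tables per group, from data the protocol already requires in the CRF. The number in each stratum will be smaller and the intervals wider. The comparison between strata is descriptive and may be confounded, for example by age within 6-35 months. The stratum for other days can also include vaccines given after the event began. The table of subjects with no other vaccine is the one to read for Fluarix Tetra, and no test between strata is needed.

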7.2.2.4. Assessment of the outcomes

Outcome of any non-serious AE occurring within 21 days post-vaccination or any SAE reported during the entire drug use investigation will be assessed as:

- Recovered/resolved.
- Not recovered/not resolved.
- Recovering/resolving.
- Recovered with sequelae/resolved with sequelae.
- Fatal (SAEs only).
- Unknown.

7.2.2.5. Medically attended visits

For each AE the subject experiences, subject/subject's parent(s)/LAR(s) will be asked if the subject received medical attention defined as hospitalisation, an emergency room visit or a visit to or from medical personnel (medical doctor) for any reason and this information will be recorded in the CRF.

7.3. Reporting of serious adverse events, adverse drug reactions and pregnancies

7.3.1. Prompt reporting of serious adverse events and other events to GSK Vaccines

SAEs will be reported promptly to GSK as described in [Table 3](#) once the physician determines that the event meets the protocol definition of an SAE.

ADRs will be reported promptly to GSK as described in [Table 3](#), if possible, once the physician becomes aware of an ADR.

Pregnancies will be reported promptly to GSK as described in [Table 3](#) once the physician becomes aware of a pregnancy in the time period defined in Section [7.2.1](#), if possible. The subject will be followed to determine the outcome of the pregnancy, if possible.

At the end of the pregnancy, whether that be full-term or premature, information on the status of the mother and child will be forwarded to GSK, if possible. Generally, follow-up should be no longer than 6 to 8 weeks following the EDD, if possible.

Table 3 Time frames for submitting SAEs and other event reports related to GSK Vaccines

Type of Event	Initial Report		Follow-up of Relevant Information on a Previous Report	
	Time Frame	Documents	Time Frame	Documents
All SAEs	24 hours *	SAE Report Form	24 hours *	SAE Report Form
All ADRs	5 days **	ADR Report Form	5 days **	ADR Report Form
Pregnancies	2 weeks *	Pregnancy Report Form	2 weeks *	Pregnancy Report Form

* Time frame is allowed after receipt or awareness of the information.

** Recommended Time frame for ADR reporting for the investigators after the awareness of the information.

7.3.2. Contact information for reporting serious adverse events and other events to GSK Vaccines

Contact for Reporting SAEs, ADRs and Pregnancies	
Please see the Local PMS Contact Information for contact details.	
Back-up Contact for Reporting SAEs, ADRs and Pregnancies	
GSK Vaccines Clinical Safety & Pharmacovigilance	[contact] or [contact] email: [contact]
GSK Korea	[contact] or [name]
DreamCIS	[contact]
24/24 hours and 7/7 days availability	

7.3.3. Completion and transmission of SAE to GSK Vaccines

Once a physician becomes aware that an SAE has occurred in a drug use investigation subject, he/she will report the information to GSK within 24 hours. The SAE Report Form will always be completed as thoroughly as possible with all available details of the event, signed by the physician (or designee), and forwarded to GSK within the designated time frames. If the physician does not have all information regarding an SAE, he/she will not wait to receive additional information before notifying GSK of the event and completing the form. The form will be updated when additional relevant information is received and forwarded to GSK within 24 hours.

The physician will always provide an assessment of causality at the time of the initial report. The causality assessment may change depending on the availability of additional/follow-up information.

Facsimile (Fax) or E-mail transmission of the SAE Report Form is the preferred method to transmit this information to the Contact for Reporting SAEs, ADRs and Pregnancies. In rare circumstances and due to failure of facsimile equipment, notification by telephone is acceptable, with a copy of the SAE Report Form sent by overnight mail. Initial notification

via the telephone does not replace the need for the physician to complete and sign the SAE Report Form within 24 hours.

In the event of a death determined by the physician to be related to vaccination, sending of the fax must be accompanied by telephone call to the Contact for Reporting SAEs, ADRs and Pregnancies.

